investigator. The investigator will retain accountability for participant's oversight and all medical decisions (i.e. protocol specified medical procedures, AE/SAE assessment and reporting, changes in medication, etc.).

As per [Section 4.6](#), during a Public Health emergency as declared by Local or Regional authorities i.e. pandemic, epidemic or natural disaster or in special circumstances, that limits or prevents on-site study visits, alternative methods of providing continuing care may be implemented by the investigator as the situation dictates. If allowed by local Health Authority and depending on operational capabilities, phone calls, virtual contacts (e.g. tele consult) or visits by site staff/home nursing staff to the participant's home can replace on-site study visits, for the duration of the disruption until it is safe for the participant to visit the site again. For more details refer to [Section 8.6](#).

Participants who prematurely discontinue iptacopan treatment for any reason during the Core treatment period should continue in the study up to Week 24 visit, completing all scheduled visits assessments. Please, refer to [Section 9.1.1](#) for details on the recommended procedures to follow in case of permanent discontinuation.

Participants who prematurely discontinue iptacopan treatment during the Extension treatment period of the study for any reason, and if possible, should continue in the study up to the Week 48 visit completing all scheduled visit assessments. The same guidance for managing iptacopan permanent discontinuation as in the Core treatment period applies ([Section 9.1.1](#)).

At this final visit, all dispensed investigational product should be reconciled, and the adverse event and concomitant medications should be recorded on the CRF.

Table 8-1 Assessment schedule – Core treatment period

Period	Screening		Core treatment period											
	Visit Name	Hb /LDH confirm.	Day 1	Day 7	Day 14	Day 28	Day 42	Day 56	Day 84	Day 112	Day 126	Day 140	Day 154	Day 168 ⁷
Visit Numbers	1	1	101	102	103	104	105	106	107	108	109	110	111	112
Days	-56 to -1	-56 to -1	1	7 ±1	14 ±1	28 ±1	42 ±3	56 ±3	84 ±3	112 ±3	126 ±3	140 ±3	154 ±3	168 ±3
Weeks	-8 to -1	-8 to -1	1	1	2	4	6	8	12	16	18	20	22	24
Informed consent	X													S
Eligibility criteria	X	X												
Demography	X													
Medical history/current medical conditions	X													
Vaccination ¹	X													
Alcohol and Smoking history	X													

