² Local reticulocytes testing can be performed at the same time as the central testing during the Screening period. In the event that the absolute reticulocytes count as assessed by the central laboratory during the Screening period is below the protocol defined threshold (absolute reticulocytes <100x10⁹/L) and only in this scenario, the results from the local lab testing can be used to determine participant's eligibility.

³ PK samples will be taken pre-dose and approximately 2h post-dose.

⁴ If the DNA sample is not taken at Day 1 visit, it can be taken at any visit thereafter.

⁵ First PRO completion should occur at a screening visit prior to Day 1 and before any other assessment at that visit.

⁶ Only FACIT-Fatigue [REDACTED] will be carried out on Day 7.

⁷ For participants not agreeing to continue in the Extension treatment period after completing Day 168 visit, End of Study will be after completing recommended procedures defined in [Section 9.1.1](#), for participants prematurely discontinuing study treatment before Day 168 but remaining in the study for abbreviated visits, please refer to [Section 9.1.1](#) for the close monitoring and additional assessments/visits to be performed in between abbreviated visits.

[REDACTED]

Table 8-2 Assessment Schedule - Extension treatment period

Period	Extension treatment Period					
	Day 196	Day 224	Day 252	Day 280	Day 308	Day336/EOS
Visit Name	201	202	203	204	205	9999 ¹
Visit Numbers	201	202	203	204	205	9999 ¹
Days	196 ± 5	224 ± 5	252 ± 5	280 ± 5	308 ± 5	336 ± 5
Weeks	28	32	36	40	44	48
Blood pressure and pulse rate	X	X	X	X	X	X
Physical examination						S
Body weight						X
Body temperature	X	X	X	X	X	X
Pregnancy test(urine)						S
Clinical Chemistry (full)		X				X
Clinical Chemistry (abbreviated)	X		X	X	X	
Hematology (full)	X	X	X	X	X	X
Coagulation/markers of thrombosis	X	X	X	X	X	X
Panel of hormones blood samples	X	X		X		X
 						
Urinalysis	X	X	X	X	X	X
Urine Albumin/Creatinine ratio			X			X
Breakthrough hemolysis				X		
MAVE				X		
 						
RBC transfusion				X		
12-lead Electrocardiogram (ECG)						X
Adverse Events				X		
Concomitant medications				X		
 						
Surgical and medical procedures				X		
Patient reported outcomes	X	X	X	X	X	X

Period	Extension treatment Period					
	Day 196	Day 224	Day 252	Day 280	Day 308	Day336/EOS
Visit Name	201	202	203	204	205	9999 ¹
Visit Numbers	201	202	203	204	205	9999 ¹
Days	196 ± 5	224 ± 5	252 ± 5	280 ± 5	308 ± 5	336 ± 5
Weeks	28	32	36	40	44	48
Iptacopan DAR				X		

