(PT)/INR, activated partial thromboplastin time (aPTT), D-dimer, and fibrinogen), [REDACTED] dipstick urinalysis, [REDACTED] and all adverse events. All data collected will be entered in the appropriate CRF page.

If treatment with iptacopan is discontinued prematurely but it is not warranted to immediately discontinue iptacopan treatment, e.g., discontinuation due to participant/guardian decision, it is recommended to consider appropriate replacement therapy based on investigator's judgment and local availability (including starting anti-C5 antibody treatment if available). In addition, it should be considered to taper down iptacopan over a period of 14 days, as follows:

- 3 capsules of 10 mg iptacopan taken in the evening (once daily) for 7 days
- 1 capsule of 10 mg iptacopan taken in the evening (once daily) for 7 days

The investigator should consider the proposed monitoring and supportive treatments listed above in case serious hemolysis occurs. For iptacopan tapering, weekly visits are recommended until one week after last iptacopan dose for the following assessments: LDH, creatinine, hemoglobin, coagulation/thrombosis markers (PT/INR, aPTT, D-dimer, and fibrinogen), [REDACTED] dipstick urinalysis, [REDACTED] and all adverse events. All data collected will be entered in the appropriate CRF page.

If discontinuation of study treatment occurs, the investigator should make a reasonable effort to understand the primary reason for the participant's premature discontinuation of study treatment and record this information.

Participants who discontinue study treatment or who decide they do not wish to participate in the study further should NOT be considered withdrawn from the study UNLESS they withdraw their consent (see 'Withdrawal of Informed Consent' [Section 9.1.2](#)).

Where possible, they should return for the assessments indicated in the Assessment Schedule. If they fail to return for these assessments for unknown reasons, every effort (e.g. telephone, e-mail, letter) should be made to contact the participant/pre-designated contact as specified in the lost to follow-up section. This contact should preferably be done according to the study visit schedule.

Participants who permanently discontinue study medication during the Core treatment period, should complete the visits as scheduled up to Week 24.

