Participants who permanently discontinue study medication during the Extension treatment period, and if possible, should complete the visits as scheduled up to Week 48.

If the participant cannot or is unwilling to attend any visit(s), the site staff should maintain regular telephone contact with the participant, or with a person pre-designated by the participant. This telephone contact should preferably be done according to the study visit schedule.

After study treatment discontinuation, at a minimum, in abbreviated visits, the following data should be collected at clinic visits or via telephone/email contact:

- New / concomitant treatments
- Safety laboratory assessments
- Adverse Events / Serious Adverse Events

All dose changes must be recorded on the appropriate CRF. The investigator must also contact the IRT to register the participant's discontinuation from study treatment.

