The primary analysis of primary endpoint is the assessment of the proportion of patients reaching the status of responder (as defined in [Section 2.5.1](#)). The lower bound of the two-sided 95% confidence interval of the response rate obtained from primary analysis will be compared to a threshold of 15%. Lower bound of the two-sided 95% confidence interval $\geq 15\%$ is sufficient for demonstration that iptacopan improves hematological response in PNH patients with hemolysis and anemia in the absence of transfusions. The derivation of the threshold is explained in [Section 5.2.2.3](#).

2.5.3 Handling of missing values not related to intercurrent event.

For the primary response definitions, RBC transfusion will qualify the participant as a non-responder, hence missing hemoglobin data after meeting the criteria for transfusion or after receiving a transfusion during Day 14 to Day 168 does not impact the primary analysis.

Missing hemoglobin data due to withdrawal from study in the core treatment period in the event that a participant did not have a prior RBC transfusion, will be imputed in a multiple imputation framework based on pattern mixture models. This aims to be consistent with the inclusion of hemoglobin data under the treatment policy strategy following all other intercurrent events. The need for transfusion will then be derived from this imputation with imputed values ≤ 9 g/dL (≤ 8 g/dL for Chinese population) considered sufficient to warrant a transfusion. This means assuming conservatively that all patients with imputed hemoglobin between 9 g/dL and 7 g/dL (between 8 g/dL and 6 g/dL for chinese patients) would have presented symptoms warranting transfusion.

- For participants withdrawing from study after discontinuation of iptacopan, the model implemented will recover a return to pre-treatment levels of Hb. This would be implemented by imputing missing values from a normal distribution with mean and standard deviation derived from all baseline hemoglobin values.
- For participants with intermittent missing data, their missing data will be handled with a missing at random approach and imputed consequently.

The model for imputation will be Markov chain Monte Carlo (MCMC) method and only baseline hemoglobin will be included in the imputation model.

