2.6.2 Handling of missing values for secondary endpoints

Missing data during study follow up will be imputed following the same principles as for the primary estimands/endpoints: intermittent missing data will be imputed according to the missing at random (MAR) principle. Missing data due to withdrawal from the study or discontinuation for iptacopan treatment will be imputed by recovering a return to pre-treatment levels. This would be implemented by imputing missing values from a normal distribution with mean and standard deviation derived from all baseline values. In case of intermittent missing data, their missing data will be handled with a missing at random approach and imputed consequently.

The model for imputation will be Markov chain Monte Carlo (MCMC) method, and only baseline values will be included in the imputation model.

For the transfusion avoidance endpoint the handling of missing data will be very similar to the handling of missing data for the primary endpoints and the same multiple imputed datasets can be used.

For the specific case of missing hemoglobin due to withdrawal, the imputation will reflect whether or not data were missing following a transfusion.

In the case of definitive withdrawal of study follow up following a transfusion only hemoglobin levels at visits during 30 days following the transfusion and until treatment discontinuation would be imputed under the MAR assumption. The missing hemoglobin after treatment discontinuation will be imputed by recovering a return to pre-treatment levels of hemoglobin. This would be implemented by imputing missing values from a normal distribution with mean and standard deviation derived from all baseline values. More specifically a patient should be first imputed in the hypothetical scenario for hemoglobin until end of treatment. In case of definite withdrawal of study follow up without transfusion missing data will be imputed as stated in [Section 2.5.3](#).

In all estimation based on a longitudinal model, missing data will be imputed multiple times. The imputed datasets will be used in the estimation of the longitudinal model. Where both intercurrent events (as for the hypothetical estimand estimating hemoglobin levels) and missing data are imputed or where only missing data are imputed, the model estimation will be derived using Rubin's combination rules.

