5.2 Statistical models

5.2.1 Tabular view of estimands and associated estimation methods

Table 5-1 Overview of estimands and estimation methods

Estimand	Endpoint	Handling strategy of intercurrent events				Summary measure
		Discontinuation of study medication	Breakthrough hemolysis events	MAVEs	RBC transfusions	
Primary estimands						
Primary estimand	composite of: increase in Hb levels ≥ 2 g/dL from baseline* without requiring RBC transfusions [#]	Treatment policy Missing data on iptacopan after study discontinuation imputed using “return to pre-treatment”	Treatment policy	Treatment policy	Not an intercurrent event- included in the composite estimand	Proportion of responders
Sensitivity analysis (Primary)1	composite of: increase in Hb levels ≥ 2 g/dL from baseline* without requiring RBC transfusions [#]	Treatment policy Missing hemoglobin central lab data replaced by local lab data at same visit. Missing data on iptacopan after study discontinuation imputed using “return to pre-treatment”	Treatment policy	Treatment policy	Not an intercurrent event- included in the composite estimand	Proportion of responders
Sensitivity analysis (Primary) 2	composite of: increase in Hb levels ≥ 2 g/dL from baseline* without requiring RBC transfusions [#]	Treatment policy Missing data on iptacopan after study discontinuation imputed using “return to pre-treatment” Considering the need for transfusion derived from imputation with imputed values ≤ 7 g/dL (≤ 6 g/dL for Chinese	Treatment policy	Treatment policy	Not an intercurrent event- included in the composite estimand	Proportion of responders

Estimand	Endpoint	Handling strategy of intercurrent events				Summary measure
		population) to be sufficient to warrant a transfusion.				
Sensitivity analysis (Primary) 3	composite of: increase in Hb levels ≥ 2 g/dL from baseline* without requiring RBC transfusions [#]	Treatment policy Missing data on iptacopan after study discontinuation imputed using “return to pre-treatment” Considering administered imputation	Treatment policy	Treatment policy	Not an intercurrent event-included in the composite estimand	Proportion of responders
Supplementary estimands						

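### For the primary endpoint, the conservative hemoglobin imputation is tied to leaving the study rather than to stopping iptacopan, so off-drug participants still in follow-up fall outside it

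*SAP*

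**What the plan says.** **Imputation for the primary endpoint.** SAP 2.5.3 has two rules for Hb that is missing without a prior transfusion.
- The conservative rule: "For participants withdrawing from study after discontinuation of iptacopan, the model implemented will recover a return to pre-treatment levels of Hb". Values are drawn from a normal distribution with the mean and SD of all baseline Hb values.
- The other rule: "For participants with intermittent missing data, their missing data will be handled with a missing at random approach and imputed consequently". It carries no on-drug condition.

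The imputation is by MCMC, with baseline Hb as the only named variable. SAP Table 5-1 repeats the study-level trigger for the primary estimand: "Missing data on iptacopan after study discontinuation imputed using" a return to pre-treatment.

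**Imputation for the secondary endpoints.** SAP 2.6.2 says it follows the same principles as the primary, but its trigger is wider: "Missing data due to withdrawal from the study or discontinuation for iptacopan treatment will be imputed by recovering a return to pre-treatment levels".

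**Who counts as withdrawn.** Protocol 9.1.1 says that participants who stop study treatment, or no longer wish to take part, "should NOT be considered withdrawn from the study UNLESS they withdraw their consent". SAP 2.3.1 plans to count those who stop treatment but stay in the core period.

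**What is collected off drug.** Protocol Section 8 says discontinuers "should continue in the study up to Week 24 visit, completing all scheduled visits assessments". Table 8-1 footnote 7 nevertheless provides "for participants prematurely discontinuing study treatment before Day 168 but remaining in the study for abbreviated visits", and 9.1.1 sets a floor: "After study treatment discontinuation, at a minimum, in abbreviated visits, the following data should be collected at clinic visits or via telephone/email contact". The floor is concomitant treatments, safety laboratory assessments and adverse events. Those who cannot or will not attend are to be contacted by telephone.

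**Limit on MAR.** Protocol 12.4.4 confines MAR to intermittent gaps whose reasons are assumed unrelated to response or compliance. SAP 2.5.3 does not carry that limit over.

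**The concern.** The primary estimand handles treatment discontinuation by treatment policy, so missing off-drug Hb should be filled with values plausible for someone off drug. Under 2.5.3 as written, a participant who has stopped iptacopan, has not withdrawn and has no central-laboratory Hb does not meet the conservative rule. If the gap is filled under MAR, the values come from a model fitted mainly to people on drug, and an untreated participant can be counted as an iptacopan responder.

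The error is in the favourable direction. It falls on the primary endpoint of a single-arm study that protocol 4.1 calls pivotal for countries without anti-C5 treatment, and no control arm would absorb a shared bias. The same participant may also be handled differently for the primary and secondary endpoints.

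**Working it through.** **Step 1. Which rule applies?** Take a participant with no transfusion and no recorded transfusion criterion.

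| Situation | SAP 2.5.3 / Table 5-1 (primary) | SAP 2.6.2 (secondary) |
|---|---|---|
| Stopped drug, then left the study | Return to pre-treatment | Return to pre-treatment |
| Stopped drug, in study, gap followed by a later value | MAR, as an intermittent gap | Return to pre-treatment by the discontinuation clause, though its intermittent clause overlaps |
| Stopped drug, in study, Hb missing through Day 168 | None stated | Return to pre-treatment |
| In FAS, never dosed (foreseen in SAP 2.1.1.1) | None clearly fits | Only if withdrawn from the study |

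**Step 2. The plan's own figures.** The Table 3-1 intervals are p ± 1.96·√(p(1−p)/40). At 30% this is 0.300 ± 0.142, or 15.8% to 44.2%; at 50% the half-width is 0.1549. All four rows reproduce. The stated 96.4% is Φ[(0.40 − 0.15 − 1.96·√(0.15·0.85/40)) / √(0.40·0.60/40)] = Φ(0.1393/0.0775) = 0.964, also reproduced.

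**Step 3. All four window visits missing.** The documents give no discontinuation rate, baseline Hb distribution or on-drug rise for this population, so these inputs are assumptions.
- Response: at least three of four values with h − b ≥ 2 g/dL, and no imputed h ≤ 9 g/dL (SAP 2.5.1 and 2.5.3; non-Chinese cut-off).
- Baseline b: mean m = 7.5 to 8.5, SD 0.8 to 1.2 g/dL, truncated below 10.
- Return to pre-treatment: h drawn from N(m, SD²).
- MAR: h = m + δ + 0.5(b − m) + noise, with noise SD 1.5 and within-person correlation 0.7.

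| Assumed mean on-drug rise δ (g/dL) | P(responder), MAR | P(responder), return to pre-treatment |
|---|---|---|
| 2 | 0.28–0.41 | 0.000–0.003 |
| 3 | 0.56–0.69 | 0.000–0.003 |
| 4 | 0.81–0.89 | 0.000–0.003 |
| 5 | 0.94–0.98 | 0.000–0.003 |

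A second set of assumptions (baseline mean 8.2, SD 1.1, truncated below 10; rises of 2.5, 3.5 and 4.5; between-person SD 1.2, within-person SD 0.6) gives 0.55, 0.81 and 0.95 under MAR against 0.0002.

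Shift per participant: 0.284/40 = 0.7 points at the low end and 0.975/40 = 2.4 points at the high end (ceiling 1/40 = 2.5). Four such participants would add about 3 to 10 points.

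**Step 4. Days 126 to 154 missing, Day 168 observed.** This is the pattern to which the MAR rule literally applies. All three missing visits must then be imputed as responses. Under the second set of assumptions the within-person correlation is 1.2²/(1.2² + 0.6²) = 0.8. If MCMC draws the visits jointly and so uses the Day 168 value, the responder probability for the three rises is:
- Day 168 at baseline: 0.001, 0.004 and 0.008.
- Day 168 at +1 g/dL: 0.04, 0.07 and 0.11.

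The largest shift is 0.11/40 = 0.3 points. Probabilities of roughly 0.4 to 0.8 arise only if the observed Day 168 value is ignored.

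**Step 5. Effect on the decision.** The criterion is a lower 95% bound of at least 15%. The Wald lower bound is 13.7% at 11/40 and 15.8% at 12/40. For the simple proportion, the percentile bootstrap lower bound is 12.5% at 10/40 and 15.0% at 11/40. The smallest passing count is therefore 11 or 12, depending on the interval. At 16/40 (40%), removing four wrongly counted responders leaves 12/40, which still passes.

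**The case against.** The strongest reply is that the intent is clear from the other texts. Protocol 12.4.4 bars MAR where missingness relates to response or compliance, and SAP 2.1 says data are analysed according to protocol Section 12. SAP section 4 lists one change from the protocol, and it is not this one. SAP 2.6.2 claims common principles and lets the primary imputed datasets be reused for transfusion avoidance. Discontinuers are asked to attend every visit to Week 24, and the abbreviated minimum includes safety laboratory tests. Anyone transfused, or recorded as meeting the criteria, is already a non-responder.

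Most of this stands. It makes the wider rule the probable intent and the affected number probably small. It does not close the gap. Section 2.5.3 is the operative text for the primary endpoint, and Table 5-1 repeats its narrow trigger. Telephone contact yields no Hb, and SAP 2.5 uses central-laboratory data only, so a local off-drug value is still missing in the primary analysis. The sensitivity analyses listed in SAP 2.5.4 and Table 5-1 (local-laboratory substitution, the 7 g/dL cut-off, administered transfusions) do not vary the MAR assumption. The tipping-point analysis of protocol 12.4.5 does not appear among them.

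A reader might infer two stronger things that the documents do not support.
- That the SAP directs all off-drug gaps to be filled as on-drug values. MAR is written only for intermittent gaps; for a gap through Day 168 the SAP is silent.
- That participants lost to follow-up also escape the conservative rule. Table 5-1 speaks of study discontinuation, which plausibly covers them.

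**Conclusion.** The gap is real, and so is the inconsistency between SAP 2.5.3 with Table 5-1, SAP 2.6.2, and protocol 9.1.1 and 12.4.4. A participant off drug, not withdrawn and without central Hb is outside the conservative rule. Depending on the pattern, that participant is either assigned MAR or left without a rule.

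Where all four window visits are missing and MAR is used by default, the reported response rate rises by about 0.7 to 2.4 percentage points per such participant in 40. This rests on the assumed baseline Hb and on-drug rise, and on the 9 g/dL cut-off. The number of such participants is unknown.

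It is tempting to claim a large inflation for the participant who returns near baseline at Day 168. That needs a literal reading in which the imputation regresses on baseline alone. Under joint MCMC the responder probability is only about 0.001 to 0.11. Nor do the documents support saying that the trial's conclusion is generally at risk: it could change only near 11 to 12 responders of 40. Otherwise the effect is on the reported rate.

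**What to change.** 1. **SAP 2.5.3 and Table 5-1, together.** Apply return to pre-treatment to every missing Hb after permanent discontinuation of iptacopan, whatever the study status, and to all missing Hb in FAS members never dosed. Restrict MAR to intermittent gaps while on iptacopan, restoring the limit in protocol 12.4.4. Changing 2.5.3 alone would leave it at odds with Table 5-1.
2. **Protocol Section 8, 9.1.1 and Table 8-1 footnote 7.** Reconcile the request for all scheduled assessments with the abbreviated visits by adding the primary-endpoint components to the existing minimum: Hb, and transfusions received or criteria met. Adverse events, safety laboratory tests and concomitant treatments stay. This cannot secure Hb from people who decline visits, so item 1 is needed in any case.

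The cost is a sentence or two in the SAP and a wording change in the protocol. No visits are added, because Section 8 already asks for them, and the sample size is unaffected. The downside is a possibly slightly lower reported response rate.
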